4.7.2.2 Main Analytical Approach

For participants in FAS, the ALSFRS-R total score as well as the change from baseline will be summarized descriptively at scheduled visits (Baseline, Week 3, Week 12 and Week 24) by treatment group. The linear mixed-effects model for repeated measures (MMRM) will be used to calculate the least square mean for each treatment group, and the treatment difference between PS matched (based on the pre-specified caliper width for main analysis) Trehalose group vs. historical control group.

The MMRM model will include the ALSFRS-R total score change from baseline at scheduled post-baseline visits as the dependent variable, with fixed effects for treatment, bulbar onset (Yes/No) and baseline value, visit (as categorical variable), treatment-by-visit interaction, and baseline value-by-visit interaction, with visit as the repeating factor, participant as a random effect. PS matched ID will also be included as a random effect for comparison between Trehalose group vs. historical control group.

The MMRM model will use restricted maximum likelihood (REML) to estimate least squares means and treatment differences. An unstructured covariance matrix will be used to model within-participant errors. Data

from all scheduled visits over the treatment period will be used to fit the model. Missing data will not be imputed.

If the computational algorithm fails to converge, the following structures will be executed in the order specified until convergence is achieved: Toeplitz with heterogeneity (TOEPH), autoregressive with heterogeneity (ARH(1)), compound symmetry with heterogeneous variances (CSH), autoregressive (AR(1)), Toeplitz (TOEP), and compound symmetry without heterogeneous variances (CS).

At the post-baseline visits of Week 3, Week 12 and Week 24, the least square mean and standard error (SE), as well as 2-sided 95% CI for each treatment group will be provided. The difference (SE) and 95% CI, p-value between PS matched Trehalose group and historical control group will be summarized.

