4.2.2 PS Estimation

PS method will be used to balance the population-level baseline characteristics between the Trehalose treated group and the eligible historical control analysis set. In order to calculate PS, the following selected common baseline demographics and characteristics variables of known prognostic significance will be used as covariates in PS estimation if applicable, other covariates may also be included.

- Age (years) [19]
- BMI (kg/m^2)
- Bulbar onset (Yes/No)
- Riluzole use (Yes/No)
- Time since ALS symptom onset (months) [19]
- Time since ALS diagnosis (months)
- Baseline ALSFRS-R total score
- Pre-baseline ALSFRS-R slope (points/month) [20]
- Baseline % predicted VC [21]

PS is the probability of a participant being assigned to a treatment instead of the other one conditional on a given set of baseline characteristics. It is determined by a logistic regression with all above common baseline covariates. To reduce any potential bias due to rare events, PS will be estimated using penalized maximum

likelihood estimation (PMLE) (Firth, 1993). The PS will be estimated for participants from Trehalose group and the eligible historical control analysis set. Overlap of PS between both groups will be assessed using standardized mean differences table and/or plot.

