4.4.2 Baseline Assessments

Descriptive statistics will be used to summarize, by treatment cohort and overall, the following baseline assessments in the FAS.

- ALSFRS-R Total Score
- ALSFRS-R Severity Group: All ALSFRS-R Items ≥ 2 , One or More ALSFRS-R Items < 2
- Pre-baseline ALSFRS-R Slope (points/month)
This equals to $(48 - \text{baseline ALSFRS-R total score}) / \text{Time since ALS symptom onset (months)}$
- % Predicted SVC
- ALSAQ – Symptom Index
- ALSAQ - Physical Mobility
- ALSAQ - Activities of Daily Living/Independence
- ALSAQ - Eating and Drinking
- ALSAQ – Communication
- ALSAQ - Emotional Reactions

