4.7.2.4 Supplementary Analyses

The following analyses will also be performed for the participants in PPS, using the same approaches as described above.

- ALSFRS-R total score summary for EAP study by treatment cohort and overall
- ALSFRS-R total score comparison between PS matched (based on the pre-specified caliper width for main analysis) Trehalose group and historical control group
- ALSFRS-R total score comparison between PS stratification-based Trehalose group and historical control group

In addition, an analysis of the total ALSFRS-R score will be performed using a general linear mixed effects model to compare the rate of decrease (ie, slope) of total ALSFRS-R scores over the 24-week treatment period between the PS matched (based on the pre-specified caliper width for main analysis) Trehalose and historical control, and between the PS stratification based Trehalose and historical control, respectively, for both FAS and PPS.

The model will fit a random intercept and slope for each participant and will include fixed effects for treatment group, bulbar onset (Yes/No), visit, and treatment by visit interaction. For comparison between the PS matched Trehalose and historical control, PS matched ID will be included as random effect; for comparison between PS stratification-based Trehalose and historical control, the PS stratification-built strata will be included as fixed effect.

An unstructured covariance structure will be used to model the within-participant errors. Visit will be expressed in weeks as a continuous variable and will include all scheduled visits including baseline as Week 0 (i.e., Week 0, Week 3, Week 12, Week 24). Missing values will not be imputed.

Estimates of the slope will be presented by the treatment group along with corresponding 95% CIs. The estimate of the difference between slopes (Trehalose vs. historical control) and the 95% CI of the difference between slopes will be presented. The null hypothesis of no difference in slopes between the treatment groups will be determined by testing the significance of the treatment by visit interaction term.

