4.7.3.2 Main Analytical Approach

For participants in FAS, the % predicted SVC (or VC) as well as the change from baseline will be summarized descriptively at Baseline and Week 24 by treatment group.

For EAP study treatment groups, an analysis of covariance (ANCOVA) model with change from baseline at Week 24 as the dependent variable, including main effects for treatment group, bulbar onset (Yes/No) and baseline value will be performed. The % predicted SVC change from baseline's least square mean (SE) and 2-sided 95% CI for each treatment group will be provided at Week 24.

For comparison between PS matched (based on the pre-specified caliper width for main analysis) Trehalose group vs. historical control group, a linear mixed effects model will be used, including the % predicted VC change from baseline at Week 24 as the dependent variable, with fixed effects for treatment group, bulbar onset (yes/no), and baseline value, with propensity score matched ID as the random effect. At Week 24, the % predicted vital capacity change from baseline's least square mean (SE) and 2-sided 95% CI for PS matched Trehalose and historical control groups will be presented. The difference (SE) and 95% CI, p-value for PS matched Trehalose vs. historical control will be summarized.

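### The matched ALSFRS-R and VC models leave out pre-baseline ALSFRS-R slope, so chance imbalance in prior decline goes uncorrected and intervals are somewhat wider than needed

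*SAP*

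**What the plan says.** SAP 4.2.2 lists nine covariates for the PS and describes them as "common baseline demographics and characteristics variables of known prognostic significance will be used as covariates in PS estimation if applicable". They are age, BMI, bulbar onset, riluzole use, time since symptom onset, time since diagnosis, baseline ALSFRS-R, pre-baseline ALSFRS-R slope and baseline % predicted VC. SAP 4.4.2 defines the slope as 48 minus the baseline total score, divided by months since symptom onset.

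The outcome models that follow use few of these:

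- Main matched ALSFRS-R model (4.7.2.2): "with fixed effects for treatment, bulbar onset (Yes/No) and baseline value, visit (as categorical variable", with treatment-by-visit and baseline-by-visit terms. Pairing enters as follows: "PS matched ID will also be included as a random effect for comparison between Trehalose group vs. historical control group".
- Main matched VC model (4.7.3.2): "with fixed effects for treatment group, bulbar onset (yes/no), and baseline value, with propensity score matched ID as the random effect".
- Supplementary ALSFRS-R slope model (4.7.2.4): "fixed effects for treatment group, bulbar onset (Yes/No), visit, and treatment by visit interaction", with the baseline score entering as the Week 0 outcome.
- Sensitivity models (4.7.2.3, 4.7.3.3): the same approach with other calipers, or with PS strata as a fixed effect.

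Balance after matching is summarised with standardized mean differences (SMDs) (4.2.3, 4.4.3). No threshold is set and no action follows from the result.

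**The concern.** Prior rate of decline is the covariate closest in meaning to change in ALSFRS-R, and the SAP itself treats it as prognostic. Baseline score does not stand in for it. By the SAP's own formula, two people who both score 36, one 12 months and one 36 months from onset, have slopes of 12/12 = 1.0 and 12/36 = 0.33 points per month, yet the main ALSFRS-R model treats them alike if bulbar onset agrees.

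Matching on one score balances covariates on average over many matched sets. It does not make the two members of a pair alike on each covariate, and a random effect for pair does not remove within-pair differences in slope. In the one matched set that is analysed, any remaining imbalance in prior decline enters the treatment difference. The outcome variance that slope explains also stays in the error term.

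The supplementary slope model is the most exposed. Bulbar onset enters only as a main effect, so no covariate adjusts the rate of decline, and imbalance in prior rate passes into the treatment-by-visit term.

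**Working it through.** **1. The plan's own figures.** The only power figures concern NfL (Protocol 9.0, SAP 6): n = 70, SD 0.30 on the log scale. A two-sided one-sample t-test at 5% gives more than 99.9% power for a 30% decline and 94.0% for a 12% decline (effect −ln 0.88). Both statements reproduce, but they do not bear on ALSFRS-R or VC. Neither document gives an SD or R² for those endpoints, so everything below is a range under assumptions.

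**2. Covariate count.** Each main model contains two of the nine PS covariates (bulbar onset and the endpoint's own baseline) and omits seven. Prior slope is among the seven in both.

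**3. Simulation A.** Assumed: 70 treated, 500 controls, nine covariates, caliper 0.2 SD of the logit PS, about 67 pairs, a generic 24-week change, 1,500 matched sets per correlation. The partial correlation is that of prior slope with 24-week change.

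| Assumed partial correlation | 0.3 | 0.4 | 0.5 |
|---|---|---|---|
| Mean reported SE, without slope | 0.852 | 0.855 | 0.852 |
| Mean reported SE, with slope | 0.814 | 0.783 | 0.737 |
| Fall in reported SE (1 − ratio) | 4.5% | 8.4% | 13.5% |
| Actual error (RMSE), without slope | 0.848 | 0.818 | 0.753 |
| Actual error (RMSE), with slope | 0.832 | 0.795 | 0.715 |
| Fall in RMSE (1 − ratio) | 1.9% | 2.8% | 5.0% |
| Equivalent extra pairs, (RMSE ratio)² − 1 | 3.9% | 5.9% | 10.9% |
| Excess of reported SE over RMSE, without slope | 0.5% | 4.5% | 13.1% |

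A paired-difference analysis (300 sets) gave SE falls of 4%, 7% and 12%.

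**4. Simulation B, built separately.** Assumed: 70 treated, 400 controls, the same caliper rule, a single Week 24 outcome, random pair intercept fitted by REML, 600 runs per scenario, about 67 pairs. The expected SE ratio is √(1 − partial R²).

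| Partial R² of slope | Formula | Simulated SE ratio | Run-to-run SD, without → with slope |
|---|---|---|---|
| 0 | 1.000 | 1.002 | 0.1748 → 0.1755 |
| 0.05 | 0.975 | 0.977 | 0.1719 → 0.1691 (−1.6%) |
| 0.10 | 0.949 | 0.953 | 0.1728 → 0.1683 (−2.6%) |
| 0.20 | 0.894 | 0.901 | 0.1602 → 0.1544 (−3.6%) |
| 0.30, other covariates 0.10 | n/a | 0.875 | 0.1494 → 0.1416 (−5.2%) |

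With R² = 0, adding all the covariates gives an SE ratio of 1.009, about 1% wider. Without slope, the mean reported SE divided by the run-to-run SD lay between 0.95 (0.1669/0.1748) and 1.04 (0.1554/0.1494). An SD from 600 runs carries about 3% Monte Carlo error (1/√1200). So the 13% excess in A at correlation 0.5 is not seen in B, where a random pair term is fitted.

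**5. Residual imbalance.** In B the slope SMD after matching had an SD of about 0.10. Its absolute value exceeded 0.1 in 29% to 36% of runs (about 32% in A). For slope R² of 0.05 to 0.30, the estimate without slope moved by −0.24 to −0.51 residual SD per unit of SMD, and by −0.11 to 0.11 with slope. An SMD of 0.1 therefore shifts the unadjusted estimate by 0.1 × 0.24 = 0.024 to 0.1 × 0.51 = 0.051 residual SD, against an SE of about 0.16 to 0.17. Averaged over runs, the estimate lay within 0.01 SD of zero.

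**The case against.** The strongest case against has five parts.

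- **The gain is small and unsourced.** No R² is in the documents. Slope is computed from baseline ALSFRS-R and time since onset, and the first is already in the main ALSFRS-R model, so what slope adds is uncertain. This stands, and the size can only be given as a range. Slope is a ratio of the two, however, so a linear term for baseline does not capture it.
- **Matching already does much of the work.** With 67 per group, simple randomisation would give an SMD with SD √(2/67) = 0.17, above 0.1 in absolute value about 56% of the time. The matched sets are tighter than that. This stands too, and it is why true error falls less than the reported SE.
- **The plan has other checks.** Alternative calipers and PS stratification are planned. Neither is triggered by the balance result, and neither adds slope to a model.
- **PS covariates need not be adjusted for twice.** Leaving them out is not an error. But the ALSFRS-R and VC models keep bulbar onset, itself a PS covariate, so the SAP already accepts adjusting after matching.
- **The analyses are exploratory.** SAP 2 says so and puts the weight on estimation. Differences, intervals and p-values are still reported, and SAP 1 allows for use in a regulatory submission. A more precise estimate serves that purpose.

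Some stronger readings are tempting, and the material does not support them:

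- A reader might infer that no PS covariate is adjusted for. Two are.
- A reader might square the SE ratios and claim 10%, 19% and 33% more pairs. Part of that fall only removes an overstated SE; the RMSEs give about 4%, 6% and 11%.
- A reader might assume all nine covariates exist for both groups. SAP 4.2.2 makes their use conditional, SAP 4.2.1 lets controls qualify on ALSFRS-R and/or VC, and Protocol 6.2.1 lets fully remote participants omit SVC.

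**Conclusion.** The point holds as a modest loss of precision and a missing prespecified correction. The two main matched models adjust for two of nine PS covariates and omit pre-baseline slope, as does the supplementary slope model, and the balance checks lead to no adjustment.

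Under assumed partial correlations of 0.3 to 0.5, adding slope cuts the reported SE by about 4% to 13% and true error by about 2% to 5%, equal to about 4% to 11% more pairs. In simulation A the unadjusted SE is conservative by about 0.5% to 13%; B, with a random pair term, shows at most about 4%, so the upper end is uncertain. If the covariates add nothing, the SE rises about 1%.

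A reader might infer that the matched estimate is biased. The calculations do not show that: mean bias is near zero, and the issue is chance imbalance in the single realised set. Pool size, caliper, covariate shift and correlations are assumptions. The outcome simulated was generic, so the size for VC is less certain still.

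**What to change.** Prespecify pre-baseline ALSFRS-R slope as a covariate:

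- in SAP 4.7.2.2, with slope-by-visit;
- in SAP 4.7.2.4, with slope-by-time;
- in SAP 4.7.3.2, as a main effect;
- in the PS-stratified versions of the same models.

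Add age and time since symptom onset where they are in the final PS model. Any covariate in the PS must be present for every matched participant, so tying the list to the final PS loses nobody.

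Do not add baseline % predicted VC to 4.7.3.2, where it is already the baseline value. Add it to the ALSFRS-R models only if it is in the final PS. Missing data are not imputed there, so otherwise matched participants could be lost.

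The cost is SAP wording and a few degrees of freedom. In the repeated-measures model, slope with slope-by-visit takes three parameters for three post-baseline visits, and age and time since onset one each as main effects. No new data are needed. The list should be fixed before the post-match balance tables are seen, since covariates chosen afterwards would be post hoc.

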4.7.2 ALSFRS-R

4.7.2.1 Definition of Endpoints

The endpoint is the mean change from baseline in ALSFRS-R total score measured at Week 24.

The ALSFRS-R is a validated instrument for evaluating the levels of the functional status of participants with ALS in 4 areas, including bulbar, gross motor activity, fine motor activity, and respiratory functions. The scale includes 12 functional items, and each item is rated on a 0 to 4 scale, with a maximum total score of 48. A higher score indicates greater retention of function. The total score collected in eCRF will be used for the analysis.

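### The last three fallback covariance structures in the ALSFRS-R MMRM force equal variance across visits; if one is ever used, the model-based Week 24 standard error is too small

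*SAP*

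**What the plan says.** SAP section 4.7.2.1 sets the ALSFRS-R endpoint: "The endpoint is the mean change from baseline in ALSFRS-R total score measured at Week 24". The model in section 4.7.2.2 uses all three post-baseline visits: "The MMRM model will include the ALSFRS-R total score change from baseline at scheduled post-baseline visits as the dependent variable". Estimates are reported at each of them: "At the post-baseline visits of Week 3, Week 12 and Week 24, the least square mean and standard error (SE"), with 95% CIs and a p-value for trehalose against historical control.

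The first-choice covariance is clear: "An unstructured covariance matrix will be used to model within-participant errors". If it does not converge, a fixed order follows. The first three alternatives allow a separate variance at each visit: "Toeplitz with heterogeneity (TOEPH), autoregressive with heterogeneity (ARH(1)), compound symmetry with heterogeneous variances (CSH"). The last three do not: "autoregressive (AR(1)), Toeplitz (TOEP), and compound symmetry without heterogeneous variances (CS").

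Two further features matter. The model is described "with visit as the repeating factor, participant as a random effect. PS matched ID will also be included as a random effect" in the matched comparison. On estimation, the section says "The MMRM model will use restricted maximum likelihood (REML) to estimate least squares means and treatment differences". It names no empirical standard error for any step of the fallback.

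Sections 4.7.2.3 and 4.7.2.4 carry this approach over to the sensitivity and per-protocol analyses. Section 2 makes all of these comparisons exploratory, with no formal hypothesis testing.

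**The concern.** In a progressive disease where people decline at different rates, scores spread out over time, so change from baseline varies least at Week 3 and most at Week 24. The SAP takes this view itself: its supplementary ALSFRS-R model in section 4.7.2.4 has a random intercept and slope for each participant. A structure with one common variance averages the three visits. It overstates the uncertainty at Week 3 and understates it at Week 24, the endpoint visit.

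Random intercepts for participant and matched pair do not repair this, because each adds the same amount of variance at every visit. At stake are the Week 24 standard errors, confidence intervals and p-value, which would err in the anti-conservative direction.

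**Working it through.** **No stated figure to reproduce.** Neither document gives an SD, slope SD, correlation, dropout rate or power for ALSFRS-R. The only power figures concern NfL (SAP section 6). They reproduce: with n = 70 and SD 0.30, power is 94.0% for a 12% decline (stated: above 90%) and above 99.9% for a 30% decline (stated: above 99%). With 13 per arm, difference 0.065 and SD 0.048, power is 91.2% (stated: 90%). They do not bear on this point.

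**Inputs.**
- Visit times: 3, 12 and 24 weeks at 7 days per week and 30.4375 days per month (SAP section 4.1), so t = 0.690, 2.760 and 5.520 months.
- Assumed: slope SD b = 0.3–1.2 points/month, visit error SD s = 1–3 points, between-person baseline SD 6 points.

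**Variance of change, given baseline.**

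v(t) = b²t² + s² + s²·36/(36 + s²)

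The last term is the baseline error that remains after adjusting for baseline. The slope term is (24/3)² = 64 times larger at Week 24 than at Week 3.

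**Effect of a common variance (CS, complete data, treatment-by-visit terms).**

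r = model SE / true SE at Week 24 = √[mean(v3, v12, v24) / v24]

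Type I error of a nominal two-sided 5% test = 2[1 − Φ(1.96 r)]

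**Worked case, b = 0.7, s = 1.5.** The noise part is 2.25 + 2.25·36/38.25 = 4.37. The slope part is 0.49·t² = 0.23, 3.73 and 14.93. So v = 4.60, 8.10 and 19.30, with mean 10.67. Then r = √(10.67/19.30) = 0.743 and type I error is 14.5%. At Week 3 the error runs the other way: √(10.67/4.60) = 1.52.

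| b | s | SD of change, Weeks 3 / 12 / 24 | r | Week 24 SE too small by | Type I error |
|---|---|---|---|---|---|
| 0.3 | 3.0 | 4.03 / 4.11 / 4.35 | 0.957 | 4% | 6.1% |
| 0.5 | 2.0 | 2.78 / 3.08 / 3.90 | 0.843 | 16% | 9.8% |
| 0.7 | 1.5 | 2.14 / 2.85 / 4.39 | 0.743 | 26% | 14.5% |
| 0.9 | 1.0 | 1.54 / 2.85 / 5.16 | 0.682 | 32% | 18.2% |
| 1.2 | 1.0 | 1.63 / 3.60 / 6.77 | 0.668 | 33% | 19.0% |

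The first and last rows are the extremes of the assumed grid.

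**The other two structures.** Using the large-sample limit of the misspecified fit over the same grid with complete data, r is 0.740–0.957 for TOEP and 0.697–0.958 for AR(1). With an assumed 25% dropout, CS gives 0.623–0.953.

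**Simulation check of CS** (60 per arm, REML, 300 data sets per scenario, no pair effect):

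| b | s | Dropout | Model SE / empirical SD | Ratio | Type I error |
|---|---|---|---|---|---|
| 0.3 | 2.0 | 0% | 0.543 / 0.559 | 0.97 | 8% |
| 0.5 | 2.0 | 0% | 0.601 / 0.726 | 0.83 | 11% |
| 0.7 | 1.5 | 0% | 0.601 / 0.827 | 0.73 | 14% |
| 0.9 | 1.5 | 25% | 0.744 / 1.045 | 0.71 | 18% |

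The direction is the same throughout.

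**Does a sandwich SE repair it?** In a separate simulation (60 per group, dropout before Week 24, CS, 400 data sets per scenario, no pair effect), type I error with model-based SEs was 11%, 14% and 16% in three scenarios. With sandwich SEs it was 5.5%, 4.5% and 4.8%.

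**Can the rule be reached?** Three visits give six distinct variances and covariances. The unstructured matrix uses all six, so a participant intercept on top is a seventh parameter that cannot be identified. TOEPH plus an intercept uses 5 + 1 = 6. ARH(1) and CSH plus an intercept each use 4 + 1 = 5, which is fewer than six.

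**The case against.** The strongest reply is that the plan already largely protects itself. It starts with an unstructured matrix and tries three heterogeneous structures before any equal-variance one, and nothing changes if any of those four converges. In simulations of growing-variance data (60 per group, 25% dropout, three scenarios of 200 data sets), all four converged every time. The Week 24 model SE was 0.98–1.00 of the empirical SD for CSH, 0.93–1.02 for ARH(1) and 0.92–1.00 for TOEPH. With participant and pair intercepts added, CSH and ARH(1) converged in all 120 further data sets. These runs are not the SAS fit on the real data, but they make the contingency look remote. This part of the objection stands.

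A reader might infer from the redundant participant effect that the equal-variance structures will be reached. The documents do not support that: the redundancy makes failure of the first choice more likely, but the next steps still have visit-specific variances. The phrase may also only mean that participant is the subject of the repeated measures, in which case there is no redundancy.

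A reader might also put one figure, such as 20–30%, on the shortfall. That is a fair middle value under moderate assumptions, but it needs ALSFRS-R variances that neither document contains. Under CS it corresponds to a Week 24 to Week 3 SD ratio of roughly 1.6–2.6.

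Finally, the comparison is exploratory, and the random-slope analysis in section 4.7.2.4 is a planned cross-check that allows growing variance, although it estimates slope rather than Week 24 change. This limits the consequence but does not remove the defect: the SE, CI and p-value will still be reported, and SAP section 1 says the results might enter a regulatory submission.

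**Conclusion.** The point holds as a conditional one. AR(1), TOEP and CS impose a single variance that conflicts with the SAP's own random-slope model. If the fallback reaches any of them, the model-based Week 24 SE is too small.

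The direction follows from random slopes; the size does not follow from the documents. The range of about 4–33%, with type I error of about 6–19%, is for CS with complete data and depends entirely on the assumed slope and error SDs. TOEP and AR(1) behave similarly, and dropout tends to widen the shortfall.

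The documents do not support saying that the ALSFRS-R analysis as planned has wrong error bars: the first-choice model and the first three fallbacks do not impose equal variance. This is a minor point, worth fixing because it is cheap.

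**What to change.** Make two changes in SAP section 4.7.2.2, which then carry to the analyses that borrow its approach.

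1. State that if AR(1), TOEP or CS is used, standard errors, confidence intervals and p-values come from the empirical (sandwich) estimator. Cluster on PS matched ID in the matched comparison, with participants nested within pair, because the pair is the independent unit there. Cluster on participant otherwise. Keep the three structures only as a last resort on these terms; deleting them would leave no specified model if CSH failed.
2. Drop the participant random effect and let the within-participant covariance matrix carry that correlation. This removes the redundancy with the unstructured matrix and a likely cause of first-choice non-convergence. Keep the matched-ID effect.

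The cost is a sentence or two in the SAP and the EMPIRICAL option in PROC MIXED. Sandwich standard errors are slightly less stable with about 70 pairs or fewer, but only when the fallback is used. They correct the standard error only: if dropout depends on earlier scores, a wrong covariance can also shift the estimate, which is a reason to keep the heterogeneous structures ahead in the order.
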